1.1.6. Study Population and Number of Participants

Adult subjects between 18 and 60 (inclusive) years of age of both sexes will be eligible for the study if they have untreated, rifampicin-sensitive, bacteriologically confirmed, *Mycobacterium tuberculosis* pulmonary TB, without other clinically significant medical conditions (including extra-thoracic TB and active eye disease) or ECG abnormalities, are not of childbearing potential or are using effective methods of birth control, are capable of and willing to provide informed consent. Human Immunodeficiency Virus (HIV) positive subjects may be enrolled if CD4+ T-cell count is ≥ 350 cells/ μ L and there is no Acquired Immune Deficiency Syndrome (AIDS)-defining opportunistic infection or malignancy. The complete list of inclusion and exclusion criteria can be found in Sections 5.1 and 5.2.

Candidates will be screened to achieve 90 randomized study participants. Within each dose escalation cohort, 18 participants will be randomly assigned to TBA-7371 (N=15) or HRZE (N=3). The total sample size of the HRZE group (all cohorts combined) will be 15, assuming all cohorts will be allowed to undergo treatment.

Within each cohort, there will be no replacement for the first 2 early withdrawals (drop-outs) occurring during the Study Treatment Phase. Drop-outs from the 3rd subject onwards will be replaced to ensure that the total number of participants completing study treatment in each cohort is at least 16. Participants who withdraw prematurely during the Follow-up Phase will not be replaced.

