9.2. Sample Size Determination

Approximately 90 participants will be randomized 5:1 to either intervention arm, totaling $N = 15$ for each TBA-7371 treatment and control groups.

Bactericidal effect

Based on Diacon et al. (2013)³, standard deviations associated with $BA_{CFU}(0-14)$ were relatively consistent across 5 treatment groups, ranging from 0.05 to 0.08. If we assume conservatively that the true SD of the $BA_{CFU}(0-14)$ measures for the TBA-7371 treatment groups is equal to 0.1, then with $N=15$ per group we have 80% (90%) power to detect a true group mean $BA_{CFU}(0-14)$ reduction of 0.067 (0.079), using a 1-sided alpha = 5%. For reference, the observed $BA_{CFU}(0-14)$ reduction in Diacon et al, 2013³ were 0.040, 0.056, 0.077, 0.104, and 0.112 for Bedaquiline 100 mg, 200 mg, 300 mg, 400 mg and standard HRZE, respectively.

Safety

With $N=15$ per group, we have approximately 80% (90%) probability to observe at least one AE if the true AE rate is 10% (15%). We have only 54% probability to observe at least one AE if the true AE rate is 5%. Across the five TBA-7371 treatment groups ($N=75$), we have 90% probability to observe at least one AE if the true AE rate is 3.0%.

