9.4. Statistical Analyses

A detailed statistical analysis plan (SAP) centered on primary and secondary endpoints will be developed and finalized prior to initiation of enrollment and will further describe the participant populations to be included in each analysis, details of the statistical methods, including procedures for accounting for missing, unused, and spurious data. Primary and secondary analyses are summarized in Table 9.

Exploratory endpoint analyses will be described in a separate exploratory scientific SAP(s) (exploratory SSAP). Specific objectives and hypotheses related to exploratory biomarker analyses will be documented in this exploratory SSAP prior to full data unmasking and analysis.

Results from the exploratory analyses may be reported in a separate results memo and included as an addendum to the clinical study report (CSR).

Table 9. Summary of Primary and Secondary Endpoints and Analyses

Endpoint	Statistical Analysis
Primary Bactericidal Effect	
Slope i.e. average change per day from screening (“0”) to Day 14 [$BA_{CFU}(0-14)$] of the log CFU counts.	For each patient, linear and bilinear regression models will be fit, and the better fit model based on lower AIC will be used to estimate [$BA_{CFU}(0-14)$] of log CFU counts from screening to Day 14. The log CFU screening measurement used in the model will be the average of the two individual screening measurements. An ANCOVA model will be used to quantify the evidence that each of the treatment group mean $BA_{CFU}(0-14)$ is less than 0 (i.e., that the treatment group mean has a negative slope on average). Multiplicity will be handled by means of a step-down sequential approach. The study will be declared a success if at least one of the TBA-7371 treatment groups achieves a statistically significant 1-sided p-value and demonstrates an acceptable safety profile.
Primary Safety	
Frequency of study participants who experienced one or more severe AEs and/or SAEs	The frequency of patients who experienced one or more severe and/or serious AE will be summarized by treatment group.
Secondary Bactericidal Effect	

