9.4.1.2. Secondary Bactericidal Activity Analyses

EBA measures (BA_{CFU}(0-2) and BA_{CFU}(2-14)) will be calculated from the regression models and assessed similarly as described above for BA_{CFU}(0-14). MGIT TPP and concentrations of LAM will also be assessed similarly. For all secondary EBA measurements there will be no adjustment for multiple comparisons and no formal success criteria.

All efficacy analyses will be performed in the mITT population, with sensitivity analyses performed in the per-protocol population to assess the robustness of results.

One of the limitations of the primary analysis method is that each individual subject must have enough data to fit a bilinear regression model in order to be included in the primary analysis. More sophisticated statistical models, such as a Bayesian nonlinear mixed-effects regression model ¹³ do not have this same limitation, and will therefore be examined through sensitivity analyses to assess the robustness of the primary model fits. The Bayesian model jointly fits the data from all patients and treatment groups and comprises the joint bilinear regression model as a special case. In addition, similar bilinear and linear regressions will also be fit directly to the change from screening response variable to further assess the robustness of the results.

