7 STUDY POPULATIONS

7.1 Populations for Analyses

Analysis populations are show in Table 6.

Table 6. Populations for Analyses

Population	Description
Randomized population	All participants randomly assigned to study intervention, who either have randomized date or randomization number.
Modified intention to treat (mITT) efficacy population	All participants randomly assigned to study intervention, who received at least one dose of the study intervention. Participants will be analyzed according to the intervention they actually received.
Per Protocol (PP) efficacy population	All participants randomly assigned to study intervention, who received the study intervention, and did not substantially deviate from the protocol procedures. Participants who substantially deviated will be identified prior to database lock. Participants will be analyzed according to the intervention they actually received.
Safety population	All participants randomly assigned to study intervention and who received at least one dose of the study intervention. Participants will be analyzed according to the intervention they actually received.
PK population	All participants who received at least one dose of TBA-7371 and have at least one pair of pre- and post-dose blood samples with measurable concentrations.

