where the parameters α and κ are the intercept and node parameter of the regression curve, respectively, the slopes β_1 and β_2 characterize the line of decline on or before the node ($t \leq \kappa$) and after the node ($t > \kappa$), respectively, and ε is the error term assumed to be independently distributed normally with mean zero and variance σ^2 . The parameters are constrained to aid in convergence as such: $\alpha > 0$, $1 < \kappa < 14$, $\sigma^2 > 0$, all $\in \mathbb{R}$. The SAS PROC NLMIXED procedure will be used to fit the bilinear regression model for individual participants in each treatment group. Suggested starting values for the parameters are $(\alpha, \beta_1, \beta_2, \kappa) = (6, 0, 0, 2)$ however a grid search approach can be followed to obtain sensible starting values. See SAS code in the Appendix which uses a grid search and picks the best fitting model.

If the bilinear regression model is selected, the average change in \log_{10} CFU/mL per day over 14 days will be estimated for each participant i by:

$$BA_{CFU}(0-14)_i = [\hat{\kappa}_i \hat{\beta}_{1i} + (14 - \hat{\kappa}_i) \hat{\beta}_{2i}] / 14$$

where $\hat{\beta}_{1i}$ is the estimated slope prior to the estimated inflection point $\hat{\kappa}_i$, and $\hat{\beta}_{2i}$ is the estimated slope after the estimated inflection point $\hat{\kappa}_i$. The parameters of main interest include the slopes $\hat{\beta}_{1i}$ and $\hat{\beta}_{2i}$, and the inflection points, $\hat{\kappa}_i$, and can be readily estimated using least squares. BA_{CFU}(0-14) can be estimated in PROC NLMIXED directly.

In the case where a subject does not have a non-missing measurement at Day 14, we have that

$$BA_{CFU}(0 - t_{last})_i = [\hat{\beta}_{1i} + (t_{last} - \hat{\kappa}_i) \hat{\beta}_{2i}] / t_{last}$$

where t_{last} is the last time point at which CFU was observed.

However, it is also likely that some of the participant specific \log_{10} CFU/mL count vs. time profiles will be better characterized using a simple linear regression model.

The form of the simple regression linear model is given by:

$$\log_{10} CFU/mL = \alpha - \beta_1 \cdot t + \varepsilon$$

where the parameters α and slope β_1 are the intercept and the slope that characterize the linear decline, and ε is the error term assumed to be independently distributed normally with mean zero and variance σ^2 . The SAS PROC NLMIXED procedure will also be used to fit a simple linear

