regression model for individual participants in each treatment group in order to ensure the Akaike information criteria (AIC) values for the linear and bilinear models are based on the same form of the likelihood function. Suggested starting values for the parameters are $(\alpha, \beta_1) = (6, 0)$ however a grid search approach can be followed to obtain sensible starting values.

If the linear regression model is selected, the average change in $\log_{10}\text{CFU}/\text{mL}$ count per day over 14 days will be estimated by the constant linear regression slope estimate, $\hat{\beta}_{1i}$, i.e.

$$BA_{CFU}(0 - 14)_i = \hat{\beta}_{1i}.$$

Therefore, for each participant, slopes will be estimated using both bilinear and simple linear regression models, and the better fit model based on lower AIC will be selected for that participant and used to estimate $BA_{CFU}(0-14)$. The $\log_{10}\text{CFU}/\text{mL}$ screening measurement used in the model will be the average of the two individual screening measurements. $BA_{CFU}(0-14)$ will be calculated for each participant within a treatment group individually, and then used as the response variable in an ANCOVA model, with a fixed effect for treatment group and screening $\log_{10}\text{CFU}/\text{mL}$ count as a covariate. Treatment group means from the ANCOVA model will be used to quantify the evidence that each of the treatment group mean $BA_{CFU}(0-14)$ is less than 0 (i.e., that the treatment group mean has a negative slope on average). The mITT population will be used for the primary efficacy analysis with analyses using the per-protocol population performed to assess the robustness of results. The SAS PROC MIXED procedure will be used to fit an ANCOVA model.

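### The SAP enters early leavers' BA(0-t_last) in the unweighted primary ANCOVA with no minimum follow-up, so Day 2-3 leavers concentrated in one regimen can distort that regimen's test and possibly its estimate

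*Protocol*

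**What the plan says.** Protocol Table 9 (section 9.4) makes the target the average change per day in log CFU from screening to Day 14. For each patient, "linear and bilinear regression models will be fit, and the better fit model based on lower AIC will be used to estimate" that slope.

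SAP 11.1.1 adds a rule that Table 9 does not contain. "In the case where a subject does not have a non-missing measurement at Day 14, we have that" BA(0-t_last) in place of BA(0-14), where t_last is the last day with a CFU result. The Appendix 4 code carries the same rule. No minimum t_last or number of points is given. Each participant's value is then "used as the response variable in an ANCOVA model, with a fixed effect for treatment group" and screening log CFU as covariate. The PROC MIXED code has no WEIGHT statement.

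The mITT population is "All participants randomly assigned to study intervention, who received at least one dose of the study intervention" (SAP 7.1), and SAP 9.4.3 does not impute missing efficacy data. A participant with two or three days of CFU data therefore stays in.

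Protocol 9.4.1.2 reads differently: "each individual subject must have enough data to fit a bilinear regression model in order to be included in the primary analysis". It gives no number of points, the SAP does not repeat the condition, and SAP section 8 reports no change from the protocol's analyses.

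On withdrawals, protocol 1.1.6 says "there will be no replacement for the first 2 early withdrawals (drop-outs") in each cohort of 18. Later ones are replaced, but anyone already dosed remains in mITT.

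**The concern.** A slope measured over two or three days is far less precise than one measured over fourteen, and if killing is biphasic it also measures something else: the early rate. The plan treats both as equal observations of BA(0-14).

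Short profiles could cluster in one regimen. Cohorts enrol in sequence, and after a safety pause everyone who has missed more than one treatment day is withdrawn (protocol 7.1), so the loss falls on whichever regimen is then being dosed. Contaminated cultures are set to missing (SAP 11.1.1), which can pull t_last earlier than the day of leaving. The decision is sensitive to one regimen, because the efficacy part of the success criterion needs only one significant TBA-7371 group.

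**Working it through.** **The plan's own figure.** Protocol 9.2 assumes that the SD of BA_CFU(0-14) "measures for the TBA-7371 treatment groups is equal to 0.1" and claims 80% (90%) power for a "reduction of 0.067 (0.079), using a 1-sided alpha = 5" per cent. A one-sample t test with n = 15 has noncentrality 0.067 x sqrt(15)/0.1 = 2.59 and 0.079 x sqrt(15)/0.1 = 3.06, which gives 79.4% and 89.7%. The figure is reproduced. It assumes 15 equally precise slopes.

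**Inputs.** From the documents: 15 per group; six groups (five regimens and pooled HRZE); daily sputum; screening value the mean of two samples; SD 0.1 for planning and 0.05-0.08 in the cited bedaquiline study. Assumed: residual SD of one log10 CFU value 0.4 (range 0.3-0.5); complete-series SD from 0.057 (between-patient slope SD 0.05) to about 0.1; leaving unrelated to outcome. The kappa x beta1 term is used as in the SAS code. It is absent from the t_last formula as printed, which is a separate matter.

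**Precision of a Day 2 value.** With three points the value is (y2 - y0)/2, so its sampling SD is 0.4 x sqrt(1 + 1/2)/2 = 0.245. A 15-point straight line has about 0.4/sqrt(280) = 0.024. Adding between-patient variation, the quantities entering the ANCOVA are sqrt(0.245^2 + 0.05^2) = 0.250 against 0.057 (4.4-fold), or 0.263 against 0.098 near the planning SD (2.7-fold).

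**Effect on the test, no activity, k leavers in one regimen.** Let s_c be the SD of a complete-series value and s_L that of a leaver's value.
- True variance of the regimen mean: [(15 - k) s_c^2 + sum s_L^2]/225.
- Variance the ANCOVA uses: {[(90 - k) s_c^2 + sum s_L^2]/90}/15.
- Rejection rate: about Phi(-1.663 x SE/SD), with 83 df.

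One Day 2 leaver, s_c = 0.057: SD = sqrt[(14 x 0.00325 + 0.0625)/225] = 0.0219. SE = sqrt[(89 x 0.00325 + 0.0625)/90/15] = 0.0161. The ratio is 1.36, so Phi(-1.22) = 11%.

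One Day 2 leaver, s_c = 0.098: SD = sqrt[(14 x 0.0096 + 0.0692)/225] = 0.0301. SE = sqrt[(89 x 0.0096 + 0.0692)/90/15] = 0.0262. The ratio is 1.15, so Phi(-1.45) = 7.4%.

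If every group has the same leavers, the pooled variance equals the regimen's own variance, the ratio is 1 and the inflation disappears.

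Monte Carlo runs with linear and bilinear fits, AIC choice and equal weights agree:

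| Leavers | One-sided rejection, nominal 5% |
|---|---|
| One regimen, one on Day 2 | 6.3-10.8% (complete-series SD 0.07-0.10); 10.0-12.6% (between-patient SD 0.05) |
| One regimen, one on Day 3 | 5.3-7.6% (SD 0.07-0.10) |
| One regimen, two on Day 2 | 8.3-15.5% (SD 0.07-0.10) |
| One regimen, Days 2 and 3 | 8.4% (SD about 0.1) to 13.7% (SD 0.057) |
| One regimen, two on Day 5 | 5.3-6.8% (SD 0.07-0.10) |
| One regimen, two on Day 7 | 5.0-5.8% (SD 0.07-0.10) |
| Same number in all six groups | 4.7-5.6% |

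The Group 1 Hochberg error with two Day 2 leavers in one regimen is 6.8-12.2%.

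**Effect on the estimate.** Shift = sum over leavers of [BA(0-t_last) - BA(0-14)]/15. Simulated estimates are compared with the run without leavers, because AIC selection alone moves the estimate.
- Flat profile: shift 0.
- -0.20/day to Day 2, then -0.05: BA(0-14) = (-0.40 - 0.60)/14 = -0.071. Each Day 2 leaver shifts the mean by (-0.20 + 0.071)/15 = -0.009. Simulated: -0.063 with none, -0.072 with one (+15%), -0.082 with two (+29%).
- -0.25/day to Day 2, then -0.04: BA(0-14) = (-0.50 - 0.48)/14 = -0.070. One Day 2 leaver shifts it by (-0.25 + 0.070)/15 = -0.012. Simulated: -0.061 to -0.074 with one (+21%), and -0.060 to -0.080 with leavers on Days 2 and 3 (+33%).
- 0 to Day 2, then -0.08: BA(0-14) = -0.96/14 = -0.069. Each Day 2 leaver shifts it by +0.005, towards zero. Simulated: -0.072, -0.068, -0.063.

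**Model choice.** With three points the bilinear line fits exactly, so AIC has nothing to choose on. With four points an exact fit, given kappa > 1, needs the two second differences to share a sign, which occurred in about a quarter of pure-noise series.

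**Alternatives.** Excluding the leavers returns the error to 4.5-4.8%. A precision-weighted random-slope estimate, approximating SAP 11.1.3.2, gives 4.1-4.6% with two leavers on Day 2, 3 or 5. Under the first fast-then-slow profile it moves only from -0.060 to -0.063 with two Day 2 leavers.

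**The case against.** Very early leaving should be rare. Protocol 7.2 expects withdrawal to be uncommon, participants stay in hospital to Day 15 with observed dosing, and the first scheduled on-treatment COVID test is on Day 7 +/- 2, when a short profile does little harm. The two unreplaced withdrawals are per cohort of 18, HRZE included. This lowers the probability, but it does not supply a rule for the case.

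The SAP already has the random-slope model of 11.1.3.2, which uses all CFU points, so a disagreement would be visible. That stands in part. However, the model is a sensitivity analysis and cannot change the success decision, SAP 11.5 appears to place it in the per-protocol population, and the other CFU sensitivity analysis (11.1.3.1) repeats the last-time-point rule.

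A reader might infer more than the documents support:
- That one or two early leavers in every regimen inflate the error. They do not; the level stays near 5%.
- That the rule always exaggerates activity. The SAP says only that profiles may be biphasic. A flat profile gives no bias and a slow start gives the opposite. Leaving because of worsening could also reverse the direction; this was not simulated.
- That a Day 2 slope is ten times as variable as a complete one. That holds for sampling error alone; the ANCOVA values differ 2.7- to 4.4-fold.
- That AIC is degenerate for any series of four points. That holds only for three.

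**Conclusion.** The point holds in this limited form. The SAP states a rule that can give a wrong primary result, and it sits uneasily with protocol 9.4.1.2. With no activity and leavers in one regimen only, the nominal 5% test rejects about 6 to 11% with one Day 2 leaver (12.6% in the most adverse setting tried) and about 8 to 15% with two on Days 2-3. The lower ends belong to the plan's own SD of 0.1. The inflation is small by Days 5-7. If early killing is faster, the estimate is steepened by roughly 15 to 20% with one Day 2 leaver and 30 to 35% with two on Days 2-3. All sizes rest on the assumed residual SD of 0.3-0.5 and on leaving being unrelated to outcome.

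**What to change.** In SAP 11.1.1, state a minimum follow-up for an individual BA_CFU value, for example CFU results to at least Day 7, and align it with protocol 9.4.1.2. Fit only the straight line when there are too few points for a bilinear fit. Run the 11.1.3.2 model in the mITT population, and say so in 11.5, so that early leavers contribute according to their information.

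Alternatively, keep everyone in the ANCOVA and add a WEIGHT statement with w = 1/(tau^2 + sigma^2 x c), where c is computed from the participant's actual sampling days for the slope used. The shortcut c = 1.5/t_last^2 is unsuitable: at Day 14 it implies a sampling SD of 0.4 x sqrt(1.5)/14 = 0.035, against about 0.023 for the fitted slope.

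The cost is SAP wording and, for the alternative, one code statement. The downside is that very early leavers count for less in the primary test, or enter only through the mixed model. The weights would also rest on two estimated variances, and a sigma^2 taken from a straight-line model absorbs any curvature.

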9.4.1. Bactericidal Activity Analyses

9.4.1.1. Primary Bactericidal Activity Analyses

The primary endpoint will be the slope of the log CFU counts from screening to Day 14 [$BA_{CFU}(0-14)$], i.e., average change in log CFU count per day over 14 days, where sputum is collected twice during the screening phase and daily thereafter. The \log_{10} CFU counts vs. time profiles over 14 days of treatment may be biphasic, i.e. the rate of change in \log_{10} CFU changes over time. A simple solution³ is to characterize the subject-specific \log_{10} CFU count vs. time profiles using a bilinear regression model, which has been proved to fit the data of many TB bactericidal agents quite well, especially over the time interval of 14 days. However, it is also likely that the some of the subject-specific \log_{10} CFU count vs. time profiles will be better characterized using a simple linear regression model.

The average slope can be estimated for each subject, i , as the mean of the slopes over each day, i.e.,

$$BA_{CFU}(0-14)_i = \sum_{t=1}^{14} \hat{\beta}_{it} / 14,$$

where $\hat{\beta}_{it}$ is the estimated slope for subject i at time t . For each subject, slopes will be estimated using both bilinear and simple linear regression models, and the better fit model (based on lower AIC) will be selected for that subject. The log CFU screening measurement used in the model will be the average of the two individual screening measurements. If the bilinear regression model is selected, the average change in \log_{10} CFU per day over 14 days will be estimated by:

$$BA_{CFU}(0-14)_i = \sum_{t=1}^{14} [\hat{\beta}_{1i} I(t \leq \hat{\kappa}_i) + \hat{\beta}_{2i} I(t > \hat{\kappa}_i)] / 14,$$

where $\hat{\beta}_{1i}$ is the estimated slope prior to the estimated inflection point $\hat{\kappa}_i$, and $\hat{\beta}_{2i}$ is the estimated slope after the estimated inflection point $\hat{\kappa}_i$. The parameters of main interest include the slopes $\hat{\beta}_{1i}$ and $\hat{\beta}_{2i}$, and the inflection points, $\hat{\kappa}_i$, and can be readily estimated using least squares. If the linear regression model is selected, the average change in \log_{10} CFU count per day over 14 days will be estimated by the constant linear regression slope estimate, $\hat{\beta}_i$. $BA_{CFU}(0-14)$ will be calculated for each patient within a treatment group individually, and then used as the response variable in an ANCOVA model, with a fixed effect for treatment group and screening \log_{10} CFU count as a covariate. Treatment group means from the ANCOVA model will be used to quantify

the evidence that each of the treatment group mean BA_{CFU}(0-14) is less than 0 (i.e., that the treatment group mean has a negative slope on average). The mITT population will be used for the primary efficacy analysis.

Multiplicity will be handled by means of a step-down sequential approach. The five TBA-7371 treatment regimens will be divided into 3 testing groups: Group 1 = Cohort V (400 mg QD) and Cohort IV (100 TID); Group 2 = Cohort III (200 mg QD) and Cohort II (100 BID); and Group 3 = Cohort 1 (100 QD). Group 1, or the group with the highest cohort allowed by the IDMC will be tested first using a Hochberg multiplicity adjustment: if the maximum and minimum one-sided p-values are ≥ 0.05 and ≥ 0.025 , respectively, formal testing will be stopped and all cohorts below will be declared a failure; if the maximum and minimum one-sided p-values are ≥ 0.05 and <0.025 , formal testing will be stopped but the regimen with p-value < 0.025 will be declared a success; if the maximum and minimum one-sided p-values are < 0.05 and <0.025 , both cohorts will be declared a success and testing will proceed to Group 2 regimens with the same step-down approach to continue until a failed cohort is observed.

The study will be declared a success if at least one of the TBA-7371 treatment groups achieves a statistically significant 1-sided p-value and demonstrates an acceptable safety profile.

